9.2 Clinical Laboratory Evaluation

9.2.1 Hematology and Biochemistry

Hematology and biochemistry safety parameters are measured at Visit 1, Visit 4, Visit 5, Visit 6, Visit 8, Visit 9, Visit 10, Visit 12 and Visit 14 (end of treatment).

Summaries will be presented for each laboratory parameter at each visit. Change from baseline (RCT and OLE baseline) and percent change from baseline to each post-baseline visit will also be presented.

If values for any of the parameters are below or above the limit of quantification of the assay (BLQ or ALQ), then they will be included in the summary tables at the BLQ or ALQ thresholds.

Where laboratory samples are repeated, the baseline value is defined as the final recorded value prior to the first dose of IMP during the lead-in trial or prior to Visit 1 in OLE trial.

Shift tables for hematology and biochemistry parameters will be produced, based upon normal ranges and GW toxicity limits (See [Appendix 3](#)), to determine the categorical shifts from each baseline (RCT and OLE) to each post-baseline visit. Values will be categorized as ‘Normal’, ‘Low’ or ‘High’ based on normal ranges and ‘Toxically Low’, ‘Toxically Normal’ or ‘Toxically High’ based on GW toxicity limits.

For eGFR, results will be assigned to the following grades:

- Normal: >60 ml/min/1.73 m²
- Grade 1: 60 ml/min/1.73 m²
- Grade 2: ≥ 30 and <60 ml/min/1.73 m²
- Grade 3: ≥ 15 and <30 ml/min/1.73 m²
- Grade 4: <15 ml/min/1.73 m²

A separate shift table will be produced for eGFR based upon the above grades to determine the categorical shifts from baseline to each post-baseline visit.

An additional table will be produced, summarizing the number of patients meeting the following criteria:

- Alanine aminotransferase (ALT) $> 1 \times \text{ULN}$ at baseline
- Aspartate aminotransferase (AST) $> 1 \times \text{ULN}$ at baseline
- AT $> 1 \times \text{ULN}$ at baseline
- Treatment-emergent ALT $> 3 \times \text{ULN}$, $> 5 \times \text{ULN}$ and $> 8 \times \text{ULN}$
- Treatment-emergent AST $> 3 \times \text{ULN}$, $> 5 \times \text{ULN}$ and $> 8 \times \text{ULN}$
- Treatment-emergent AT $> 3 \times \text{ULN}$, $> 5 \times \text{ULN}$ and $> 8 \times \text{ULN}$
- Treatment-emergent AT $> 3 \times \text{ULN}$ and either bilirubin $> 2 \times \text{ULN}$ or INR > 1.5

where AT is AST or ALT, and treatment emergent is defined as criteria not met at baseline, but

met at any time post-baseline. The above will be summarized overall and for the following subgroups:

- Valproic acid use (as a concomitant medication) (Yes, No).
- Clobazam use (as a concomitant medication) (Yes, No).
- Valproic acid use and Clobazam use (as concomitant medications) (Yes/Yes, Yes/No, No/Yes, No/No).
(A medication will be considered concomitant if it has a start date on or after the first dose of IMP or if it was started prior to the first dose of IMP and was ongoing.)
- Patients taking 3 or more current AEDs.
- Patients taking 4 or more current AEDs.

All laboratory data will be listed; listings will include limited demographic information about the patient (age, sex, race and weight at baseline). Abnormal laboratory values will be listed separately. A further listing will be created for the laboratory reference ranges and toxicity limits. A listing of liver parameters (ALT, AST, bilirubin and INR) will be produced that includes the baseline result, result at the particular visit, change from baseline, upper limit of normal (ULN) value, ratio of result to baseline and ratio of result to ULN.

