9.1.1.10 Visit 15 (Day 739 [+ 7], End of Taper)

A visit window of + 7 days from the scheduled visit date is permitted, but it is preferred that the visit is performed on the scheduled visit day, where possible. This visit marks the end of the taper period.

Information regarding changes to concomitant medications and AEs will be reviewed. Vital sign and suicidality assessments will be performed.

The investigator must assess adherence to the dosing schedule.

All GWP42003-P (used and unused) will be collected, and a check of the returned GWP42003-P against usage should be made.

The following assessments are not required but should be performed if clinically indicated:

- Physical examination (including body weight)
- ECG
- Clinical laboratory samples (urine [where possible] and blood) will be taken for the following:
 - Hematology
 - Biochemistry

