9.1.3 Unscheduled Visits

Unscheduled visits and assessments may be performed in the event of a safety concern, as deemed necessary by the investigator. Data from any unscheduled visits should be reported on the unscheduled visits eCRF.

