6.1 Statistical Definitions and Algorithms

6.1.1 Conventions for treatment/visit naming

In all tables, listings and figures, the treatment arms will be referred to and labelled as per [Table 2](#).

Table 2 Study treatments

Endpoint	RCT Treatment	Actual Treatment	Protocol/Annex	Treatment Label (Table column/Figure legend)	Sorting order in listings, column order in tables
All	Double-Blind Treatment GWP42003-P different dosing	GWP42003-P, at different dosing	Enrolled under Protocol	Double Blind Treatment: GWP42003-P Enrolled Under Protocol	1
All	Double-Blind Treatment GWP42003-P different dosing	GWP42003-P, at different dosing	Enrolled under Annex	Double Blind Treatment: GWP42003-P Enrolled Under Annex	2
All	Double-Blind Treatment Placebo different dosing	GWP42003-P, at different dosing	Enrolled under Protocol	Double Blind Treatment: Placebo Enrolled Under Protocol	3
All	Double-Blind Treatment Placebo different dosing	GWP42003-P, at different dosing	Enrolled under Annex	Double Blind Treatment: Placebo Enrolled Under Annex	4

In all tables, listings and figures, the study visits will be referred to and labelled as per [Table 3](#).

Table 3 Study Visits

Actual Visit	Visit Label
Baseline (last record before 1 st IMP administration during lead-in trial)	RCT Baseline
Baseline (Assessment at extension Visit 1)	OLE Baseline
Visit 1: Day 1	Day 1
Visit 2: Day 8 Telephone Call	Day 8 TC
Visit 3: Day 15 Telephone Call	Day 15 TC
Visit 4: Day 29	Day 29
Visit 5: Day 57	Day 57
Visit 6: Day 85	Day 85
Visit 7: Day 141	Day 141
Visit 8: Day 197	Day 197
Visit 9: Day 281	Day 281
Visit 10: Day 365	Day 365
Visit 12: Day 547	Day 547
Visit 14: Day 729 or withdrawal	End of Treatment
Visit 15: Day 739 (end of taper)	End of Taper
Visit 16: Day 767	Follow-up

No derivation will be used for visits; data will be tabulated and listed according to the visit it was recorded under in eCRF.

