9.3 Vital Signs, Other Physical Findings and Other Safety Data

9.3.1 Vital Signs

Vital signs (systolic blood pressure, diastolic blood pressure and pulse rate) are measured at Visit 1, Visit 4, Visit 5, Visit 6, Visit 7, Visit 8, Visit 9, Visit 10, Visit 12, Visit 14 (end of treatment) and Visit 15 (end of taper).

Summaries will be presented for each vital sign parameter at each visit. Change from baseline (RCT and OLE baseline) to each post-baseline visit will also be presented.

A separate table will be produced, by visit, presenting the incidence of patients with vital signs indicative of a medical condition at Visit 1 and indicative of an AE after Visit 1.

Based on the criteria presented in [Appendix 3](#), potentially clinically significant changes from baseline (RCT and OLE baseline) in vital signs measurements and other defined flagged values will be identified at each visit. The number of patients with a potentially clinically significant change from baseline will be summarized by parameter, and visit. The number of patients with at least one post-baseline flagged vital sign parameter value will be summarized by parameter, and flagged criteria.

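### Apart from the transaminase criteria, laboratory toxicity is tabulated by visit only: no table counts patients who ever crossed a toxicity limit, and unscheduled or repeat results have no defined place

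*SAP*

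**What the plan says.** SAP 9.2.1 names the laboratory visits as Visits 1, 4, 5, 6 and then "Visit 8, Visit 9, Visit 10, Visit 12 and Visit 14 (end of treatment". It plans summaries at each visit, and shift tables against normal ranges and toxicity limits "to determine the categorical shifts from each baseline (RCT and OLE) to each post-baseline visit". A separate eGFR shift table is also built visit by visit. One further table, for ALT, AST, either transaminase, and either transaminase combined with raised bilirubin or INR, counts a patient who meets a criterion at any time after baseline. All laboratory data are listed, with a separate listing of abnormal values.

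SAP 6.1.1 sets the visit rule: "No derivation will be used for visits; data will be tabulated and listed according to the visit it was recorded under in eCRF". Table 3 in that section gives the visit labels. It has no label for unscheduled visits and omits Visits 11 and 13, but it does include "Visit 15: Day 739 (end of taper").

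Protocol V2, 9.1.3, states: "Data from any unscheduled visits should be reported on the unscheduled visits eCRF". Protocol 9.1.1.10 says of laboratory tests and other procedures at Visit 15: "The following assessments are not required but should be performed if clinically indicated".

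For vital signs, SAP 9.3.1 states: "The number of patients with at least one post-baseline flagged vital sign parameter value will be summarized". SAP 9.3.2 plans the same kind of count for ECG.

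**The concern.** Tables 10 and 11 set toxicity limits for platelets, neutrophils, haemoglobin, sodium, creatinine, bilirubin, alkaline phosphatase, gamma GT, INR and others. The natural safety question is how many patients ever crossed each limit on treatment. Outside the transaminase criteria, the SAP produces no table that answers it.

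The results least certain to be tabulated are those taken because something looked wrong. The protocol expects such samples:
- 8.1.2 calls for extra hepatic monitoring after a dose increase when no scheduled test is near.
- 9.2.9 calls for INR once ALT or AST exceeds 3 × ULN, and for haematology as well if only the hepatic panel was drawn.
- 9.2.9 also calls for repeats of clinically significant end-of-treatment abnormalities.

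A patient whose platelets fall below the limit at an unscheduled visit and recover by the next scheduled draw could show no shift at any tabulated visit. Laboratory parameters are a named component of the primary safety endpoint, and an omission of this kind can only lower the toxicity counts.

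**Working it through.** The plan states no figure for this point, so the check is mainly a tracing of each type of result through the rules.

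**1. Where each result goes**

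| Result | Governing text | Place in the laboratory tables |
|---|---|---|
| Scheduled full panel | SAP 9.2.1 visit list | By-visit summary and shift; no patient-level count |
| ALT or AST, alone or with bilirubin or INR | SAP 9.2.1 additional table | Counted at any time post-baseline |
| Bilirubin alone, INR alone, alkaline phosphatase, gamma GT | SAP 9.2.1, Tables 10 and 11 | By visit only |
| Unscheduled | Own eCRF form (Protocol 9.1.3); tabulated as recorded (SAP 6.1.1) | No label in Table 3, so no assigned column |
| Repeat after baseline | SAP 9.2.1 repeat rule covers the baseline value only | Value to use is undefined |
| Hepatic panel at Visits 11 and 13 (valproic acid, or dose above 15 mg/kg/day) | Protocol Appendix 1 | Visits absent from Table 3 and from the 9.2.1 list |
| Hepatic panel at Visit 7 (same patients) | Protocol Appendix 1 | Labelled in Table 3, absent from the 9.2.1 list |
| Visit 15, if clinically indicated | Protocol 9.1.1.10; SAP Table 1 | Labelled in Table 3 and marked in the schedule, absent from the 9.2.1 list |

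**2. Why by-visit counts do not give the number of patients**

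The 9.2.1 list has eight visits after Visit 1 (4, 5, 6, 8, 9, 10, 12, 14). If one patient is beyond a limit at each of them, the number of patients ever beyond the limit is anything from 1 (the same patient each time) to 8 (a different patient each time). So the gap exists even if no unscheduled sample is ever taken.

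**3. How likely a transient episode is to overlap the next scheduled full panel**

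Scheduled full-panel days (SAP Table 1): 1, 29, 57, 85, 197, 281, 365, 547, 729.

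Gaps: 28, 28, 28, 112, 84, 84, 182, 182 days.

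Assume that onset is uniform within a gap and that the abnormality lasts *d* days. The chance that it is still present at the next draw is min(1, *d* / gap).

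| Gap | *d* = 14 | *d* = 28 | *d* = 56 |
|---|---|---|---|
| 28 days | 14/28 = 50% | 28/28 = 100% | 100% |
| 84 days | 14/84 = 17% | 28/84 = 33% | 56/84 = 67% |
| 112 days | 14/112 = 13% | 28/112 = 25% | 56/112 = 50% |
| 182 days | 14/182 = 8% | 28/182 = 15% | 56/182 = 31% |

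The durations are assumptions, and the ±7-day visit windows are ignored. The table shows where scheduled draws alone are a weak net: little is lost up to Day 85 for episodes of four weeks or more, and considerably more is lost afterwards.

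**The case against.** The strongest reply is that important off-schedule findings do reach a primary safety table. Adverse events are the first component of that endpoint, and the protocol's definition of an adverse event covers relevant abnormal laboratory findings (12.1.1). Results considered to be adverse events must be entered on the eCRF whenever they occur (9.2.9). SAP 6.1.8.1 treats every event outside the break between the two trials as treatment-emergent, and 9.1 tabulates those events. This stands. A reader might infer that off-schedule toxicities appear in no summary of the primary endpoint, and the documents do not support that. What remains are toxic values that the investigator does not judge to be adverse events. A judgement of that kind is not a count against pre-set limits.

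Two other strong readings also fail. The first is that Visit 15 laboratory results are excluded. They are missing from one list, but Visit 15 is labelled in Table 3 and marked as optional for laboratory tests in the SAP schedule, so the text is ambiguous. The second is that unscheduled and repeat values are dropped. The SAP gives no rule for them and never says that it drops them. The table shells are a separate document and may settle some of this.

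The vital-sign and ECG sections do not mention unscheduled values either. The contrast with them is between patient-level and by-visit counting, and to that extent it holds.

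Finally, the SAP does not depart from the protocol, whose 13.6.2.4 asks only for end-of-treatment summaries, change from baseline and shift tables. Nor is any hypothesis tested.

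**Conclusion.** The point holds as a gap in the laboratory summaries. Followed exactly, the SAP yields no number of patients ever beyond a Table 10 or 11 limit, or with a worsened eGFR grade, outside the transaminase criteria. It also leaves the handling of unscheduled, repeat, Visit 11, Visit 13 and Visit 15 results to be settled in programming after database lock. Any resulting bias is towards fewer laboratory toxicities.

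The size cannot be stated, because the documents give no event rate. The overlap chances suggest a small effect where draws are 28 days apart and a larger one where gaps are 84 to 182 days. It would be tempting to take the complement of the 182-day row as the share of off-schedule findings that no table shows. That does not follow: the calculation is not conditional on detection off schedule, it picks the two longest gaps, and some of those findings enter the adverse event tables. How many patients reach the second year is also unclear. The SAP Overview says the extension is stopped prematurely, while 9.5 says that patients complete it per protocol and annex.

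This is an inexpensive improvement to a primary safety summary. It does not affect trial conduct.

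**What to change.** Keep the by-visit tables. Add to SAP 9.2.1, for every parameter with a normal range or toxicity limit (including bilirubin, INR, alkaline phosphatase and gamma GT) and for eGFR, one shift table from baseline category to worst post-baseline category. Show worst low and worst high separately and count each patient once. State that all post-baseline results contribute, including unscheduled and repeat samples and those from Visits 7, 11, 13 and 15. In the same section, say which value the by-visit tables use when a post-baseline sample is repeated, and bring the 9.2.1 visit list, Table 3 and the schedule into agreement on Visits 7, 11, 13 and 15.

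The cost is SAP wording and one extra table per panel, from data already collected and listed. Toxicity counts will look somewhat less favourable. No new sample or procedure is needed, and because the SAP is to be finalised before any descriptive analysis, the change can still be pre-specified.

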9.2.9 Clinical Laboratory Sampling

The investigator should use his/her judgment and knowledge of the patient to determine when to best collect the blood and urine samples in order to mitigate the risk that invasive procedures may cause the patient to become stressed, thereby affecting the results of other patient assessments.

Routine laboratory tests will include hematology, biochemistry, and urinalysis (provided urine can be obtained), IGF-1 levels, and a serum pregnancy test (if appropriate). Analysis of all clinical blood samples and pregnancy tests will be conducted at a central clinical laboratory.

Urine samples for biochemistry will be analyzed at the trial center by use of a dipstick, with any relevant findings being sent for further urinalysis at the central laboratory (urinalysis, microscopy, culture, and sensitivity, as applicable). In cases where urine samples cannot be analyzed at the center due to local regulations, a full set of urine samples should be sent to the central laboratory for analysis. Urine sample volume requirements and processing procedures will be detailed in a separate laboratory manual.

The investigator and trial monitor will be provided with a list of the normal ranges used by the testing laboratory for all variables assayed during the trial and a statement of accreditation (or similar) for the laboratory.

The investigator should be aware of blood sampling volume restrictions, particularly for patients with low weight, and if additional monitoring is required (maximum total daily volume of 0.85mL/kg of body weight^{68,69} maximum 4-week period volume of 2.55 mL/kg of body weight, and maximum 8-week period volume of 50 mL).

Clinical laboratory sample parameters are detailed in [Table 9.2.9-1](#).

Study Code: GWND19002
 EudraCT Number: 2019-001605-24
 Clinical Protocol V2 18Dec19

Table 9.2.9-1 Biochemistry, Hematology, and Urinalysis			
Biochemistry (Serum)¹	Hematology (Whole Blood)¹	Urinalysis (Urine)²	Pregnancy Test (Serum)¹
Alanine aminotransferase ³	Hematocrit	Blood	Serum
Albumin ³	Hemoglobin	Glucose	
Alkaline phosphatase ³	Mean cell volume	Nitrites	
Aspartate aminotransferase ³	Mean corpuscular hemoglobin	pH	
Calcium	Platelets	Protein	
Creatine kinase	Red blood cell count	White blood cells	
Creatinine	White blood cell count with automated differential	Bilirubin	
Creatinine clearance	Prothrombin time and INR (plasma) ⁵	Ketones	
Gamma-glutamyl transferase ³		Specific gravity	
Glucose		Urobilinogen	

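### The eGFR scale in SAP 9.2.1 gives Grade 1 no width, so its shift table registers no decline that stays above 60 ml/min/1.73 m²

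*SAP*

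**What the plan says.** SAP 9.2.1 (Hematology and Biochemistry) sets five eGFR categories. The top one is open-ended: "Normal: >60 ml/min/1.73 m²". The line beneath it carries neither an inequality sign nor a range: "Grade 1: 60 ml/min/1.73 m²". The other three are ranges in the same units: Grade 2 takes values of at least 30 but under 60, Grade 3 values of at least 15 but under 30, and Grade 4 anything under 15.

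The use to be made of them is explicit: "A separate shift table will be produced for eGFR based upon the above grades to determine the categorical shifts from baseline to each post-baseline visit".

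The same section plans other displays. Each laboratory parameter is summarised by visit, and "Change from baseline (RCT and OLE baseline) and percent change from baseline to each post-baseline visit will also be presented". Hematology and biochemistry shift tables are built on two schemes, the laboratory normal ranges (Low, Normal, High) and the sponsor's toxicity limits. All laboratory data are to be listed, with abnormal values listed separately.

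The biochemistry panel in Protocol 9.2.9 includes creatinine and "Creatinine clearance" but not eGFR, and neither document gives an eGFR formula. Clinical laboratory parameters belong to the primary safety endpoint (Protocol 4.1.1, SAP 2.2.2).

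**The concern.** A five-level scale was evidently intended, with Grade 1 as the mild step between Normal and Grade 2. As printed only four levels do any work. The mild step has no width, and Normal extends down to just above 60, so a reader of the shift table cannot tell a stable patient from one whose eGFR has roughly halved but remains above 60.

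What is at stake is how the table will be read. A Grade 1 row at or near zero looks like a finding that mild decline was looked for and hardly seen, when the row could scarcely be filled.

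**Working it through.** **Could the printed line have lost a sign?** The inequality signs on the four neighbouring lines are intact. Restoring one to Grade 1 does not help:

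- at least 60, or above 60: overlaps Normal
- at most 60, or below 60: overlaps Grades 2 to 4
- from 60 to some higher bound: overlaps Normal

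No single restored sign or bound gives a usable Grade 1 while Normal stays at above 60. The Normal line would have to change as well.

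**Width of each category.** Applying the five rules as written to the integers 0 to 150:

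| Category | Integers held (of 151) |
|---|---|
| Normal (61 to 150) | 90 |
| Grade 1 (60) | 1 |
| Grade 2 (30 to 59) | 30 |
| Grade 3 (15 to 29) | 15 |
| Grade 4 (0 to 14) | 15 |

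On a grid of 0.1, Grade 1 holds 1 of 1,501 points. The categories do not overlap and leave no gap; the fault is only that one of them is a point.

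**Shifts as the table would report them.** Percent change = (visit − baseline) / baseline.

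| Baseline | Visit | Change | Reported shift |
|---|---|---|---|
| 120 | 90 | −25% | Normal to Normal |
| 120 | 61 | (61 − 120)/120 = −49% | Normal to Normal |
| 90 | 60.1 | −33% | Normal to Normal |
| 90 | 60 | −33% | Normal to Grade 1 |
| 90 | 59.9 | −33% | Normal to Grade 2 |
| 61 | 59 | (59 − 61)/61 = −3% | Normal to Grade 2 |
| 100 | 45 | −55% | Normal to Grade 2 |

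**How many patients could land in Grade 1?** The documents give no eGFR distribution, so this is an illustration. Assume a normal distribution with SD 20, results reported as integers, and the 252 patients that Protocol 13.1 expects. The actual number may be smaller, because SAP 1 says the trial was stopped early. Expected count = 252 × P(59.5 < eGFR < 60.5).

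| Assumed mean | Expected in Grade 1 at a visit | Share between 60 and 90 |
|---|---|---|
| 110 | 252 × 0.00088 = 0.2 | 15% |
| 90 | 252 × 0.0065 = 1.6 | 43% |
| 75 | 252 × 0.0151 = 3.8 | 55% |

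Nearly everyone in the last column is counted as Normal.

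**How far does creatinine cover the gap?** Assume that eGFR varies inversely with creatinine; the documents state no formula. A fall from 120 to 61 then multiplies creatinine by 120/61 = 1.97. On the normal-range scheme the patient ends above the upper limit (UL) only if baseline creatinine exceeded 1/1.97 = 0.51 × UL. On the toxicity scheme (SAP Table 10, at least 2.6 × UL) baseline would have to be at least 2.6/1.97 = 1.32 × UL. Whether the fall is flagged therefore depends on where the patient started.

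**The case against.** The strongest reply is that little is lost. Any fall below 60 appears as Grade 2 or worse. Creatinine has a normal-range shift table, so a rise above the laboratory's upper limit moves a patient from Normal to High long before the toxicity limit. Creatinine clearance is in the same panel and could shift to Low. SAP 4.1 puts minimum and maximum in every continuous summary, so a 49% fall would bound the minimum percent change if eGFR is summarised like other parameters. Individual results are listed, and Protocol 12.1.1 counts relevant abnormal laboratory findings as adverse events. The analysis is descriptive throughout, and the clinical safety background in Protocol 3.2.2 singles out liver enzymes rather than the kidney.

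Most of this stands, and it rules out three stronger readings that a reader might reach:

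- *That creatinine cannot help because its limit is 2.6 × UL.* That is only the toxicity scheme. The normal-range scheme applies too and is a real, though partial, backstop.
- *That Grade 1 is empty whatever the drug does.* A result of exactly 60 belongs there, and in the illustration the expected count rises from 0.2 to 3.8 as the assumed mean falls. Sparse is the right word.
- *That mild renal decline is invisible in this trial.* It is invisible in this table, and only while eGFR stays above 60.

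It is also fair to say that the documents give no eGFR lower limit of normal, so they do not show where mild reduction begins. None of this makes the printed Grade 1 workable for the table it was written for.

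**Conclusion.** The grading rule is wrong as written, at minor severity. Grade 1 is a single point, so the eGFR shift table shows no movement for declines that stay above 60, including one of 49%, and sends a 3% decline across the boundary straight to Grade 2. This follows from the printed cut-points and needs no outside assumption; only the patient counts and the creatinine comparison rest on assumptions, stated above.

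The effect is limited to one descriptive table. The documents do not support a claim that the safety analysis as a whole would give false reassurance about renal function, because the change summaries, the normal-range shifts and the listings remain. The change summaries help here only if eGFR is in fact handled as one of the laboratory parameters, which the SAP does not say in terms.

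**What to change.** Amend the eGFR lines in SAP 9.2.1 in one of two ways.

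1. **Preferred.** Define Normal as at or above the central laboratory's lower limit of normal for eGFR, and Grade 1 as at least 60 and below that limit. Grades 2 to 4 stay as they are. This uses the kind of limit on which the SAP's other laboratory shift tables already rest.
2. **If the laboratory supplies no such limit.** Delete Grade 1, assign a result of exactly 60 to the top category, and label that category as not below 60 rather than Normal. The table then makes no claim to have graded mild decline.

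In the same edit, state how eGFR is derived and whether it is included in the by-visit change summaries, since the protocol panel does not name it.

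The cost is a line or two of SAP text and a format change in one table. No data collection, visit or sample size is affected. SAP 1 says the plan is finalised before any descriptive analysis, so the correction belongs in the SAP text and should not be left to the programmer.
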